At the same time, the research team will pilot the initial iteration of the PROACTIVE parent model with foster parents of youth in the foster care programs. After foster parents complete an initial screening via REDCap survey, a member of the research team will contact the foster parent to confirm eligibility. The research team member will then obtain informed consent. After consent has been given, the foster parents will be asked to complete an initial and final assessment. Initial assessment is completed prior to attendance of parent coach sessions and the final assessment is completed after the last session.

The subjects will complete a demographics questionnaire (i.e. name, age, sex, gender, race, ethnicity, education, employment, socioeconomic status, address (for mailing payment, confirmation of state residency, and mailing consent form if requested), caseworker contact information) as part of their initial assessment. We will also ask subjects questions regarding their own parenting needs, their youth's mental health needs, and the parents' ability for engaging with mental health services.

During this initial and final assessment, the parent will complete the following measures:

- Parent-Patient Activation Measure – Mental Health
- PROMIS Parent Proxy Measure – Anxiety
- PROMIS Parent Proxy Measure – Depression
- Pediatric Symptom Checklist-17 (Parent Proxy)
- Barriers to Treatment Participation Scale
- Client Satisfaction Questionnaire (final assessment only)

Data will be collected through a REDCap survey.

Parent involvement in the intervention is anticipated to be 30-60 minutes each session (up to 10 sessions) which may occur over the course of up to 12 weeks.

Foster parents will be compensated \$20 after completing the initial assessment *and* attending the initial session. Foster parents will also be compensated \$20 after completing the final assessment. In addition, foster parents will have the ability to earn

continuing education credits necessary for foster parent licensure for completing this program.

Following the initial assessment, the caregiver will meet with a parent coach, who is an internal member of the NU research team, for 30-60 minutes each session. The content of the sessions will consist of one or more of the following:

- 1) introducing the program
- 2) identifying and setting goals
- 3) discussing results of the assessment
- 4) helping parents develop literacy regarding their child(ren)'s mental health needs

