learning new skills, learning how to locate services for their child, and obtaining referrals to providers through a publicly accessible databases. Thus, while this program fills in gaps in traditional mental health services, it does not constitute comprehensive mental health treatment, a fact that will be consistently emphasized to participants throughout both parts of the study. We will explicitly include this in the consent form and check in with participants regularly to ensure that this is understood and that participants have access to complete services. In addition, parents might feel uncomfortable sharing personal information with research study staff. In order to mitigate this risk, we will emphasize that participants do not have to answer any question they do not want to or participate in any activity that makes them uncomfortable. If they continue to feel uncomfortable, they can choose to opt out of the remainder of the needs assessment or pilot study, depending on which they are enrolled in.

18.0 Provisions to Protect Participant Privacy and Data Confidentiality:

In terms of data storage, all data will be stored on secure Northwestern servers and only accessed by members of the research team. While the data will be stored with identifiers, since the research staff will need to contact participants, data will be de-identified when downloaded. When the data is being transferred from REDCap to the M drive, it will be downloaded on an FSM computer and immediately transferred to the appropriate M drive location. The data will be stored indefinitely on the M drive and on NU's REDCap server.

In terms of delivering the pilot intervention, all coach - participant check-ins will be held using confidential video-based software (e.g. Zoom) and will be conducted in a private setting where others not involved in the research project cannot hear the advocates' conversations with participants.

19.0 Data Monitoring Plan to Ensure the Safety of Participants:

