Cover Page

Study: PROACTIVE Parent: PROviding Access To InnoVative & Evidence-Based Intervention

Date: 6/16/21

Statistical Plan

We plan to enroll 14 foster parents with 7 foster parents per condition.

For the primary outcomes: acceptability, usefulness, and feasibility we will conduct descriptive analyses separately for the post-session items and the post-intervention Customer Satisfaction Survey. We will sum relevant items on the post-session questionnaires (administered after each of the 10 sessions) and provide mean ratings for program Acceptability, Usefulness, and Feasibility. We will provide mean ratings for Acceptability, Usefulness, and Feasibility from the Customer Satisfaction Survey. We will also provide descriptive statistics for other aspects of Feasibility as described below.

For the primary Treatment vs. Control group analyses we will examine 2 (Group) x 2 (Time) repeated measures ANOVA, with repeated measures on the second factor (Time). For measures that include subscales we will use K (number of subscales) x 2 repeated measures MANOVA to assess for treatment effect on subscale scores. For the child outcome measures we will use 2 x 2 repeated measures MANOVA with each of the child outcome measures and/or subscale scores in one model, as the child outcomes may share some variance.

For the delayed treatment analyses, we will combine the treatment and the delayed treatment participants to examine a one-way repeated measures ANOVA examining the pre-post scores of each of the groups – essentially using T1 and T2 data for the original treatment group and the T3 and T4 data for the delayed treatment groups. We will use a one-way repeated measures MANOVA for the child outcomes.

Primary Outcomes. Primary Outcomes will be assessed with three types of measures. Post-session measures that assess session content and delivery at the end of each of the 10 sessions, post-intervention in a Customer Satisfaction Survey, and pre- and post-intervention with standardized measures.

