Parent-Patient Activation Measure – Mental Health (P-PAM-MH). We will examine change in parent activation from baseline (T1) to post-treatment (T2, week 11) in the treatment condition relative to the control condition. Parent activation will be measured using the Parent-Patient Activation Measure- Mental Health. While the study is likely not powered to detect significant differences, our goal is to estimate effect sizes. We predict that parent scores in the treatment group, relative to the control group, will increase from baseline to Time 1 (T1) to post-intervention, while scores in the control condition will remain the same from baseline (T1) to T2, week 11. We predict that parents in the delayed treatment group will demonstrate consistent scores on T1, T2 and T3 (re-assessment, prior to delivery of delayed intervention) will remain the same, but that parents will demonstrate higher scores on T4 after receiving the delayed intervention.

Family Empowerment Scale (FES). We will examine change in parent empowerment from baseline (T1) to post-treatment (T2, week 11) in the treatment condition relative to the control condition. Parent empowerment will be measured using the FES. While the study is likely not powered to detect significant differences, our goal is to estimate effect sizes. We predict that parent scores in the treatment group, relative to the control group, will increase from baseline to Time 1 (T1) to post-intervention, while scores in the control condition will remain the same from baseline (T1) to T2, week 11. We predict that parents in the delayed treatment group will demonstrate consistent scores on T1, T2 and T3 (re-assessment, prior to delivery of delayed intervention) will remain the same, but that parents will demonstrate higher scores on T4 after receiving the delayed intervention.

Secondary Outcomes.

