Pediatric Symptom Checklist-17 (PSC-17). We will examine change in child internalizing, externalizing, and attention symptoms from baseline (T1) to post-treatment (T2, week 11) in the treatment condition relative to the control condition. Child symptoms will be measured using the PSC-17. While the study is likely not powered to detect significant differences, our goal is to estimate effect sizes. We predict that child scores in the treatment group, relative to the control group, will decrease from baseline to Time 1 (T1) to post-intervention, while scores in the control condition will remain the same from baseline (T1) to T2, week 11. We predict that children of parents in the delayed treatment group will demonstrate consistent scores on T1, T2 and T3 (re-assessment, prior to delivery of delayed intervention) will remain the same, but that these children will demonstrate lower scores on T4 after parents receive the delayed intervention.

Barriers to Treatment Participation Scale (BTPS). We will examine change in parent perceptions of barriers to treatment participation from baseline (T1) to post-treatment (T2, week 11) in the treatment condition relative to the control condition. Barriers to treatment will be measured using the BTPS. While the study is likely not powered to detect significant differences, our goal is to estimate effect sizes. We predict that parent scores in the treatment group, relative to the control group, will decrease from baseline to Time 1 (T1) to post-intervention – indicating a reduction in barriers to treatment, while scores in the control condition will remain the same from baseline (T1) to T2, week 11. We predict that parents in the delayed treatment group will demonstrate consistent scores on T1, T2 and T3 (re-assessment, prior to delivery of delayed intervention) will remain the same, but that parents will demonstrate lower scores on T4 after receiving the delayed intervention.

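### The single MANOVA of all child outcomes drops a parent for one missing child score, and the documents do not say that parents who stop sessions are still assessed at T2

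*SAP*

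**What the plan says.** The SAP's Statistical Plan states: "We plan to enroll 14 foster parents with 7 foster parents per condition". The group comparison of a measure is given as: "For the primary Treatment vs. Control group analyses we will examine 2 (Group) x 2 (Time) repeated measures ANOVA". Instruments with subscales get a MANOVA across their own subscales. The child outcomes are handled together: "we will use 2 x 2 repeated measures MANOVA with each of the child outcome measures and/or subscale scores in one model". The child instruments, listed under secondary outcomes, are PROMIS anxiety, PROMIS depression and the PSC-17. That makes three scores with the PSC-17 total, or five with its three subscales. The later pooled pre-post analysis, "essentially using T1 and T2 data for the original treatment group and the T3 and T4 data for the delayed treatment groups", also uses a MANOVA for the child outcomes.

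The SAP names no missing-data method, analysis set or expected dropout. For each standardized measure it concedes low power and gives effect-size estimation as the aim. Protocol section 17.0 lets parents leave any question unanswered and says that "they can choose to opt out of the remainder of the needs assessment or pilot study".

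On timing, the SAP places T2 at week 11 for both conditions. For controls it predicts that "scores in the control condition will remain the same from baseline (T1) to T2, week 11". Protocol section 8.0 says "the final assessment is completed after the last session", with up to 10 sessions over up to 12 weeks.

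**The concern.** Repeated measures MANOVA as normally fitted works on complete cases. A parent who answers the PSC-17 and PROMIS depression but not PROMIS anxiety at T2 would contribute nothing to any child outcome, although most of the data are in hand. With 7 parents per condition, each such loss is 1/7, or 14%, of an arm.

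The second part is who has a T2 score at all. If the final assessment follows the last session, a parent who stops attending may never be asked for one. The documents neither provide for this case nor rule it out. Where the aim is to estimate effect sizes, precision and bias of the estimate are what matter, and both depend on which parents remain in the model.

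**Working it through.** **Inputs.** From the SAP: N = 14 (2 x 7), two visits (T1, T2), three child instruments. No missing-data rate is given, so every rate below is an assumption. No plan figure exists to reproduce beyond 2 x 7 = 14.

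**Step 1: parents left at T2.** Let a be the proportion missing T2 altogether and s the proportion skipping each child questionnaire, independently, with T1 complete.

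- Child MANOVA: 14(1 - a)(1 - s)^3
- Single-measure model: 14(1 - a)(1 - s)

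With a = 10% and s = 5%: 14 x 0.9 x 0.95^3 = 10.8, against 14 x 0.9 x 0.95 = 12.0.
With a = 20% and s = 10%: 14 x 0.8 x 0.9^3 = 8.2, against 14 x 0.8 x 0.9 = 10.1.

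**Step 2: effect on the confidence interval.** The 95% half-width is proportional to t(n - 2)/sqrt(n), with t the two-sided 5% critical value. The ratio of MANOVA set to single-measure set, using unrounded counts, is:

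- First case: sqrt(11.97/10.80) x 2.270/2.229 = 1.053 x 1.018 = 1.07, about 7% wider.
- Second case: sqrt(10.08/8.16) x 2.431/2.302 = 1.111 x 1.056 = 1.17, about 17% wider.

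**Step 3: how far this depends on the missingness pattern.** Let m be the missing rate. The first two columns assume independent skipping per questionnaire at both visits. The last assumes that the whole T2 survey is missed and all else is complete.

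| m | One measure, 14(1 - m)^2 | Child MANOVA, 14(1 - m)^6 | Whole T2 survey missed, either model, 14(1 - m) |
|---|---|---|---|
| 5% | 12.6 | 10.3 | 13.3 |
| 10% | 11.3 | 7.4 | 12.6 |
| 15% | 10.1 | 5.3 | 11.9 |
| 20% | 9.0 | 3.7 | 11.2 |

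The extra loss from the MANOVA ranges from none to severe, depending on whether parents skip single questionnaires or whole surveys.

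**Step 4: degrees of freedom.** With p child scores the MANOVA error df are N - p - 1. For p = 5 that is 8 at N = 14, 2 at N = 8 and 0 at N = 6, where no multivariate test is possible.

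**Step 5: what an all-available-data model gains.** A simulation used 7 per arm, T1-T2 correlation 0.5, a true effect of 0.5 SD and 20,000 runs (all assumed).

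- With 30% of T2 missing completely at random, the standard error was 0.66 SD for complete cases and 0.65 SD for a mixed model, so precision hardly changes.
- With treated-arm dropout rising with the baseline score and a flat 10% in controls, complete cases were biased by +0.18 SD and the mixed model by about 0.00.

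By symmetry, if low scorers leave instead, the complete-case bias becomes about -0.18 SD. A bias of fixed sign also means different things on different scales: the SAP predicts that activation rises and child symptoms fall.

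**Step 6: timing side by side.** A treated parent whose sessions run the full 12 weeks would have the Protocol's final assessment after week 12, which is later than the SAP's week 11. A parent who stops at session 4 has a T2 under the SAP if week 11 is applied to everyone. Under the Protocol the answer depends on what the last session means. Neither document settles the case.

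**The case against.** Several stronger readings are tempting, and the documents do not support them.

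- **That every planned model drops a parent for one missing questionnaire.** A 2 x 2 ANOVA of one measure loses a parent only for that measure, and a subscale MANOVA only within its instrument. The standardized primary measures, P-PAM-MH and FES, are not in the child model. Acceptability, usefulness and feasibility are descriptive and unaffected. Listwise deletion is the default of the named method, not a rule that the SAP states.
- **That T2 is triggered by the last session.** That sentence is in the Protocol, which describes 50 caregivers who receive the intervention and no control group. The SAP describes 14 in two conditions and fixes T2 at week 11, including for controls, who have no sessions before then. The Protocol also pays for the final assessment without stating session attendance as a condition. What stands is an inconsistency and a gap.
- **That the child intervals would be about 19% or 46% wider.** Those ratios compare the Step 1 counts with all 14 parents complete. The single-measure model is itself about 11% and 25% wider than that, and no analysis method restores data never collected.
- **That the completer analysis will favour the program.** Nothing shows that treated parents leave more often than waiting controls, or which parents leave. The 0.18 SD follows from an assumed mechanism.

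It is also fair that REDCap collection makes whole-survey non-response plausible, and that the SAP already plans to report the percentage of parents who finish every study task, though not by condition.

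These objections narrow the point. They do not answer the dependence of the child MANOVA on complete scores, or the missing rule for parents who stop.

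**Conclusion.** The point holds for the child-outcome MANOVA and for T2 ascertainment. It should be changed before analysis but does not threaten the study as a whole. Relative to a single-measure model, the interval is about 7% wider if 10% miss T2 and 5% skip each child questionnaire, and about 17% wider at 20% and 10%. Both figures assume independent skipping and complete T1 data. If parents miss whole T2 surveys, the MANOVA costs no additional parents. A change of model then mainly reduces bias where dropout relates to baseline scores, in a direction that cannot be known in advance. The documents give no attrition rate, so how many parents will be lost cannot be stated.

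**What to change.** 1. Replace the child MANOVA with a separate linear mixed model for each measure (group, time, group x time), using all available T1 and T2 scores with every parent in the assigned condition. Report the group difference in change with a 95% confidence interval. Use the same model for the other standardized measures.
2. Do not constrain the two conditions to a common baseline mean unless allocation is confirmed to be random. Neither document says that it is, and Protocol section 20.0 describes participants as individually selected.
3. Reconcile the SAP's week 11 with the Protocol's last-session wording. State that every enrolled parent is invited to the T2 assessment at the same time point in both conditions, whether or not sessions were completed.
4. Report T2 completion by condition.

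The cost is SAP and Protocol wording, a REDCap invitation to parents who have stopped, and the loss of the omnibus MANOVA test. That loss is small when the stated aim is to estimate effect sizes.

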In addition to creating the infrastructure and content necessary to support PROACTIVE Parent, this study ultimately has two aims:

1. Does the PROACTIVE Parent Program improve foster parents' capacity for supporting their youth in care's mental wellbeing?
2. Does the PROACTIVE Parent Program improve youth in cares' mental health symptoms, as reported by the foster parents?

2.0 Enrollment Criteria (who can be in your study and who would not be eligible to participate in your study):

For the needs assessment, eligible participants are foster parents of youth with a special health care need (including disabilities, mental health needs, and/or complex medical needs). Participants must be over the age of 18 and be actively fostering a child through the Illinois Department of Children and Family Services.

For the pilot study, eligible participants are foster parents of youth with identified mental health needs. Foster parents must be over the age of 18 and be actively fostering a child ages 5-13 through a child welfare agency in the United States. All participants will also need to speak English, be a resident of Illinois, and be able to navigate virtual meeting technologies (e.g. Zoom).

3.0 Sample Size:

For our needs assessment, we anticipate that 1000 caregivers involved in the specialized foster care program will complete our survey. Given that over 3000 caregivers foster youth in care with special health care needs, we believe that this is a feasible number with recruitment support from DCFS.

For our initial pilot study, we will be recruiting 50 caregivers who will receive the pilot intervention. This pilot data will be used to inform a larger iteration of the study, but we believe that 50 caregivers is sufficient for our initial pilot.

4.0 Recruitment and Screening Methods:

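### Does the pooled delayed-treatment pre-post analysis, which has no control, need to be changed or relabelled?

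*SAP*

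**What the plan says.** The Statistical Plan section of the SAP has 14 foster parents, 7 per condition, and two kinds of pre-post analysis.

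- **Controlled.** "For the primary Treatment vs. Control group analyses we will examine 2 (Group) x 2 (Time) repeated measures ANOVA". It uses T1 and T2, and the delayed group serves as the control.
- **Pooled.** A separate paragraph covers the parents who get the program after a wait. Its model is given as follows: "we will combine the treatment and the delayed treatment participants to examine a one-way repeated measures ANOVA examining the pre-post scores". The scores that enter it are then named: "essentially using T1 and T2 data for the original treatment group and the T3 and T4 data for the delayed treatment groups". For children: "We will use a one-way repeated measures MANOVA for the child outcomes".

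Each of the seven standardized measures (P-PAM-MH, FES, PROMIS anxiety, PROMIS depression, PSC-17, BTPS, DERS) has its own paragraph. Each first defines the quantity of interest as T1-T2 change under treatment compared with control. It then says "While the study is likely not powered to detect significant differences, our goal is to estimate effect sizes". Each also predicts level scores in the delayed group before that group gets the program; for P-PAM-MH, "We predict that parents in the delayed treatment group will demonstrate consistent scores on T1, T2 and T3".

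Protocol section 3.0 describes a different pilot: "we will be recruiting 50 caregivers who will receive the pilot intervention", and "This pilot data will be used to inform a larger iteration of the study". Protocol section 8.0 has only an initial and a final assessment.

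**The concern.** The pooled analysis has time as its only factor and contains no untreated interval. Natural improvement, regression to the mean and the effect of answering the same questionnaire twice all count as program effect in it. Regression to the mean is plausible, because Protocol section 2.0 enrols parents of children already known to have mental health needs.

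The SAP does not describe the pooled result as uncontrolled. It uses 14 change scores in one sample, where the controlled contrast compares 7 with 7, so its interval is half as wide. A reader of an uncaptioned table could prefer the confounded figure because it looks more precise, and could take it into the planning of a larger study.

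The T3 score, moreover, enters only as the baseline of the delayed group's treated interval. No stated analysis therefore looks at the predicted stability up to T3.

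**Working it through.** **Inputs.** From the SAP: 7 parents per condition, 14 in the pooled analysis. The SAP gives no alpha, SD, effect size or power, so it has no figure to reproduce beyond 7 + 7 = 14. Assumed: two-sided alpha 0.05, SD of each change score = 1, no dropout, no program effect, and non-program change c of 0.2, 0.3 or 0.5 SD of change.

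**1. What each analysis estimates.** Let P be the program effect.
- Pooled, c in both intervals: [7(P + c) + 7(P + c)]/14 = P + c.
- Pooled, c in T1-T2 only: [7(P + c) + 7P]/14 = P + c/2.
- 2x2 interaction, c common to both groups: (P + c) − c = P.

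**2. Precision.**
- Pooled: SE = √(1/14) = 0.267; half-width = t(13) × 0.267 = 2.160 × 0.267 = 0.58.
- 2x2: SE = √(2/7) = 0.535; half-width = t(12) × 0.535 = 2.179 × 0.535 = 1.16.

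**3. False rejection when P = 0.** With c in both intervals, the pooled test is a one-sample t test with noncentrality c√14. With c in T1-T2 only, the rates come from simulation.

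| c | Bias, both intervals | Rejects | Bias, T1-T2 only | Rejects | 2x2 bias | 2x2 rejects |
|---|---|---|---|---|---|---|
| 0.2 | 0.20 | 11% | 0.10 | 6% | 0 | 5% |
| 0.3 | 0.30 | 18% | 0.15 | 8% | 0 | 5% |
| 0.5 | 0.50 | 41% | 0.25 | 13% | 0 | 5% |

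Simulation of the 2x2 at c = 0.3 gave a mean estimate of 0.00 and rejection of 5.0%.

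**4. Child-outcome MANOVA.** This is a one-sample Hotelling test on p scores with equal change in each and correlation r between changes. The noncentrality is 14c²p/[1 + (p − 1)r], with df p and 14 − p. For p = 5 (anxiety, depression, three PSC-17 domains), c = 0.3 and r = 0.5, it is 14 × 0.09 × 5/3 = 2.1, and rejection is 11%. Over r = 0.3 to 0.7 the range is 10-14%. With p = 3 (PSC-17 total in place of its domains) it is 13-17%.

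**5. What a T1-T3 stability check could show.** With 7 parents the half-width is t(6)/√7 = 2.447/2.646 = 0.92. Power against a true change of 0.3 is 10%. Both figures assume that T1-T3 change has the same SD as the other changes. The T1-T2 part of the prediction already enters the 2x2, because the delayed group is its control arm. Only T2-T3 lies outside a stated analysis.

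**6. What the SAP puts forward as the effect.** The word primary is attached to the treatment-control comparison. All seven measure paragraphs define a contrast with control and state the estimation goal beside it. The pooled analysis sits apart, under its own name, and is described as pre-post. No sentence in either document says that its result will be called the program effect or used to plan the next study.

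**The case for a change.** The strongest case for acting is that a caption costs almost nothing. When a study exists to estimate effect sizes, it matters which figure goes forward, and the SAP does not say so in one sentence. The pooled model does lack a control, the arithmetic above is right, and a prediction made seven times is not followed through to T3. All of that stands.

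Several things weaken it.

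- The misuse it guards against is one the SAP does not propose.
- The 11%, 18% and 41% rates need the same non-program change in both intervals. Regression to the mean after selection on need may fall mainly in the first, where the rates are 6%, 8% and 13%. Rejection rates also carry little weight in a study that disclaims power.
- The 2x2 is not beyond question. Neither document describes how parents are allocated, and if natural T1-T2 change differed between groups by 0.3, the 2x2 would itself be biased by 0.3. To declare it the only usable effect would claim more than the documents support.
- A mixed model for all four times would rest on linear change that these data can hardly test, so it is no clear gain.
- The statement about informing a larger study belongs to the protocol's pilot of 50 caregivers who all receive the program, not to the SAP's 14 in two conditions.

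**Conclusion.** The description is correct: the pooled ANOVA and MANOVA measure uncontrolled within-person change. Under the stated assumptions the bias is the full non-program change if it occurs in both intervals, and half of it if it occurs only in T1-T2. The plan's main inference does not rest on this analysis, because the SAP already makes the controlled T1-T2 contrast primary and ties its effect-size goal to it.

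What remains is a gap in labelling and description. An analyst would ordinarily caption a one-group pre-post result as such and tabulate the delayed group's means at each assessment. Doing so changes no estimate, and with 7 parents the T1-T3 figures could describe stability but not confirm it. No change to the planned analysis follows.

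This conclusion assumes that the SAP's design (14 parents, two conditions, T1 to T4) is the one run. The later protocol (12/08/2021, against 6/16/21 for the SAP) has 50 caregivers, all receiving the program, with two assessments. Under that design neither the 2x2 nor the T3-T4 analysis would exist, and every pre-post estimate would be uncontrolled. That mismatch between the documents is a separate matter, and rewording the delayed-treatment paragraph would not settle it.

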PROMIS Parent Proxy Pediatric Anxiety Short Form 8a (P-P Anxiety). We will examine change in child anxiety symptoms from baseline (T1) to post-treatment (T2, week 11) in the treatment condition relative to the control condition. Child symptoms will be measured using the PROMIS P-P Anxiety. While the study is likely not powered to detect significant differences, our goal is to estimate effect sizes. We predict that child scores in the treatment group, relative to the control group, will decrease from baseline to Time 1 (T1) to post-intervention, while scores in the control condition will remain the same from baseline (T1) to T2, week 11. We predict that children of parents in the delayed treatment group will demonstrate consistent scores on T1, T2 and T3 (re-assessment, prior to delivery of delayed intervention) will remain the same, but that these children will demonstrate lower scores on T4 after parents receive the delayed intervention.

PROMIS Parent Proxy Pediatric Depressive Symptoms Short Form 8a (P-P Depression). We will examine change in child depressive symptoms from baseline (T1) to post-treatment (T2, week 11) in the treatment condition relative to the control condition. Child symptoms will be measured using the PROMIS P-P Depression. While the study is likely not powered to detect significant differences, our goal is to estimate effect sizes. We predict that child scores in the treatment group, relative to the control group, will decrease from baseline to Time 1 (T1) to post-intervention, while scores in the control condition will remain the same from baseline (T1) to T2, week 11. We predict that children of parents in the delayed treatment group will demonstrate consistent scores on T1, T2 and T3 (re-assessment, prior to delivery of delayed intervention)

will remain the same, but that these children will demonstrate lower scores on T4 after parents receive the delayed intervention.

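### The only analysis using T3 and T4 averages both groups' changes, so the SAP's T4 prediction for the delayed group gets no estimate of its own

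*SAP*

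**What the plan says.** The SAP's Statistical Plan sets enrolment: "We plan to enroll 14 foster parents with 7 foster parents per condition". It then gives two inferential analyses of the standardised measures.

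- **Primary comparison.** A Group by Time repeated measures ANOVA with two levels of each factor. The outcome paragraphs fix the contrast as change "from baseline (T1) to post-treatment (T2, week 11) in the treatment condition relative to the control condition".
- **Delayed treatment analysis.** Here "we will combine the treatment and the delayed treatment participants to examine a one-way repeated measures ANOVA", described as "essentially using T1 and T2 data for the original treatment group and the T3 and T4 data for the delayed treatment groups". For the child measures: "We will use a one-way repeated measures MANOVA for the child outcomes".

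Each standardised measure also has a prediction about the delayed group itself: stable scores over T1, T2 and T3, then improvement at T4. For the P-PAM-MH and FES the wording is "but that parents will demonstrate higher scores on T4 after receiving the delayed intervention". For the two PROMIS measures and the PSC-17 it is that "these children will demonstrate lower scores on T4 after parents receive the delayed intervention". The BTPS and DERS paragraphs predict lower parent scores at T4.

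No other analysis in the SAP uses T3 or T4.

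**The concern.** The prediction and the analysis concern different quantities. The prediction is about one group's change from T3 to T4. The analysis has time as its only factor and covers both groups together, so its single effect mixes that change with the treatment group's T1-T2 change. A pooled improvement could come largely or wholly from the treatment group, and the planned output would not show it.

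The treatment group's T1-T2 changes are also the treated side of the primary comparison. A chance high result there raises both estimates, and the SAP does not mention the overlap. The risk is that readers take the pooled result as evidence that delayed parents improved, or as support separate from the primary result.

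**Working it through.** **Inputs.** From the SAP: 7 parents per condition, the contrasts and time points above, and the stated aim of estimating effect sizes. The SAP gives no alpha, SD, effect size or power, so the only figure to reproduce is enrolment: 7 + 7 = 14, which agrees. Assumed here: SD of change 1 in each group, normal changes, no dropout and, for the significance rates, two-sided 5% tests.

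**Step 1: what the pooled model estimates.** With two time points, a one-way repeated measures ANOVA is a paired t-test on 14 changes. Let T be the treatment group's mean T1-T2 change and D the delayed group's mean T3-T4 change. Then

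pooled estimate = (7T + 7D)/14 = (T + D)/2.

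| T (SD) | D (SD) | Pooled (SD) |
|---|---|---|
| 1.0 | 0 | 0.50 |
| 1.5 | 0 | 0.75 |
| 1.0 | -0.5 | 0.25 |

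D is not a parameter of the model. This step is algebra and needs no assumption about SD or alpha.

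**Step 2: overlap with the primary comparison.** Let C be the delayed group's mean T1-T2 change. The primary estimate is T - C. Each mean change has variance 1/7. Let ρ be the correlation between a delayed parent's T1-T2 change and T3-T4 change.

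- Cov(T - C, (T + D)/2) = (1/2)(1/7)(1 - ρ) = (1 - ρ)/14.
- SD of primary × SD of pooled = sqrt(2/7) × sqrt(1/14) = 1/7.
- Correlation, primary with pooled = (1 - ρ)/2.
- Correlation, primary with delayed-only = (-ρ/7)/(sqrt(2/7) × sqrt(1/7)) = -ρ/sqrt(2).

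The SAP does not date T3 relative to T2, so ρ needs a range. If scores at all four times are equally correlated, ρ = 0. If T3 nearly duplicates T2 and the other correlations are equal at r (score variance 1), the covariance of the two changes is -(1 - r) and each has variance 2(1 - r), so ρ = -0.5.

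| Case | ρ | Primary with pooled | Primary with delayed-only |
|---|---|---|---|
| Equal correlations | 0 | 0.50 | 0 |
| T3 nearly duplicates T2 | -0.5 | 0.75 | 0.5/1.414 = 0.35 |

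**Step 3: illustrative significance rates.** Simulation with 7 per group. Only significant results in the predicted direction count as positive, so a test with no true effect is positive in 2.5% of trials.

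- No true effect, ρ = 0, given a falsely positive primary result: the pooled test is positive in about 17% of trials, a delayed-only test in about 2.4%. At ρ = -0.5 the delayed-only figure is about 9.5%.
- Treatment group +1.0 SD, delayed group 0: pooled positive in 32%, delayed-only in 2.5%. At +1.5 SD the pooled figure is 54%.

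**Step 4: precision.** The 95% half-width in SD of change is t/sqrt(n).

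- Delayed-only: 2.447/sqrt(7) = 0.92.
- Pooled: 2.160/sqrt(14) = 0.58.

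**The case against.** **The wording may intend separate looks.** The delayed-analysis sentence also mentions the pre- and post-scores of each group. That is ambiguous. But combining the participants in a one-way model describes one time effect, and the clause explaining which data are used fits that reading. If separate looks were meant, the text should say so, and the fix is the same.

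**Pooling treated pre-post pairs is normal in a delayed-treatment design.** This stands. The pooled figure is a legitimate uncontrolled summary and more precise than either group alone, and reusing data is not an error in itself. A reader might infer that the pooled analysis is invalid; the documents do not support that.

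**The SAP claims no replication and no power.** This also stands. It never calls the pooled result a second confirmation, and it says under each standardised measure that the aim is to estimate effect sizes. A reader might infer that the plan presents overlapping data as independent evidence; it does not. The effect-size aim does not remove the gap, though, because the effect size matching the T4 prediction is the delayed group's own change.

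**The significance rates are selective.** In part. They rest on an assumed alpha and SD, and the 32% and 54% figures assume a program that works in one group and does nothing in the other, which nothing in the documents suggests. They illustrate the mechanism and do not forecast a result.

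**The point may be moot.** The protocol, dated 12/08/2021 against 6/16/21 for the SAP, plans 50 caregivers who all receive the intervention (section 3.0), with one initial and one final assessment (section 8.0). It describes no control group, delayed group, T3 or T4. Which design applies has to be settled first.

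**Conclusion.** The concern holds as a mismatch between prediction and analysis. The SAP predicts a T4 change in the delayed group, and its only T3-T4 analysis estimates the average of two groups' changes. That follows from the model and the equal group sizes alone. The primary comparison is unaffected.

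The pooled result is not independent of the primary result: the correlation is 0.50 with equal correlations across times and about 0.75 if T3 nearly duplicates T2. These values assume equal SDs of change and no dropout.

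A reader might also infer that a delayed-only estimate would be a fully independent replication. The documents do not support that either. Its correlation with the primary estimate runs from 0 to about 0.35, because the delayed group's T2 and T3 scores may be closely related. It overlaps less than the pooled figure in both cases, and it addresses the stated prediction.

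**What to change.** First reconcile the SAP with the protocol on whether a control and delayed group exist. If the delayed-treatment design is kept, rewrite the delayed-treatment paragraph of the Statistical Plan as follows.

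1. For each standardised measure, report the delayed group's T3-T4 mean change with a 95% CI, and name it as the estimate for the T4 prediction.
2. If the pooled figure is kept, fit a Cohort (treatment, delayed) by Time (pre, post) model. Show both cohort changes and their difference.
3. State that the pooled figure is an uncontrolled pre-post summary that shares the treatment group's T1-T2 data with the primary comparison.
4. Do not describe the delayed-only estimate as fully independent of the primary comparison. State when T3 falls relative to T2.

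The cost is SAP wording and added lines in the results tables, with no new data or visits. The price is precision: with 7 parents, the interval that answers the stated prediction is about 1.6 times as wide as the pooled one (0.92/0.58). That is tolerable in a pilot that aims to estimate effect sizes.
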